Disease management in elderly heart failure patients. Final version #1-1-2001

A prospective, controlled study of a disease management program for elderly with heart failure.

STUDY PROTOCOL

First approved version: January, 1, 2001 Amended : December 12, 2004

Amended 12-12-2004: Financial support from an unrestricted grant from the non-profit organization: Associazione ADRIANO: Associazione Italiana per la Diffusione della Ricerca sulle Cardiopatie dell'Anziano (Program AD-HF 001-2005) (avalaible at www.associazioneadriano.it).

INDEX

- 1- Synopsis
- 2- Introduction and background
- 3- Study plan, patients and methods
- 4- Statistical analysis
- 5- Outcome variable
- 6- Variables collected
- 7- Ethical issues
- 8- Coordinating and Participating Centers
- 9- References

1.Synopsis

Elderly heart failure patients are at high risk of events. Available studies and systematic reviews suggest that elderly patients benefit from disease management programs (DMP). However, important questions are still open, including the optimal follow-up intensity and duration and whether such interventions are cost-effective during long-term follow-up and in different health care systems. The primary aim of this study is to determine the long-term efficacy of a hybrid disease management program in consecutive older outpatients. Moreover, because elderly represent a heterogeneous population, the secondary aim of this study is to determine which patients benefit mostly from a DMP, by means of their frailty profile. Intervention will consist in combined hospital- (cardiologists and nurse-coordinators from 2 heart failure clinics) and home-based (patient's general practitioner visits) care. The components of the DMP are: discharge planning, education, therapy optimization, improved communication, early attention to signs and symptoms. Intensive follow-up was based on scheduled hospital visits (starting within 14 days of discharge), nurse's phone call and home general practitioner visits. A comprehensive multidimensional assessment will be performed prospectively in all patients at baseline

2. Introduction.

Clinical management of older heart failure patients remains sub-optimal with subsequent high risk of mortality, morbility, poor quality of life and increasing costs, despite the availability of effective treatments (1-4). Available studies and systematic reviews suggest that elderly patients benefit from disease management programs (DMP) designed to improve quality of care and patient compliance and reduce hospital admissions with a beneficial cost-effectiveness ratio (5-10). However, results on other end-points and mortality are inconclusive. Furthermore, important questions are still open, including the most appropriate patient's selection process, the optimal follow-up intensity and duration and finally, whether such interventions are cost-effective during long-term follow-up and in different health care systems (7-10). Elderly patients include a heterogeneous population where the clinical status and subsequent risk profile result from a complex interaction between different domains (8): age-related cardiovascular changes, cardiovascular disease, comorbid conditions, age-related impairments and social issues (9). Multidimensional assessment (MA) is a validated diagnostic process to determine the medical, psychological, and functional capabilities and aimed at providing information for appropriate choice of care-plan and follow-up. One of the major goals of the MA is the identification of frailty. Frailty is a clinically recognized syndrome of loss of reserves (energy, physical ability, mobility, cognition, health) that gives rise to an increased vulnerability to stressors (e.g., concomitant acute illnesses, hospitalizations, medical procedures) and the risk of major events such as low-compliance, falls, disability, hospitalization and death, in subjects with or without HF. Although the focus of MA is the frail or disabled elderly, this approach was rarely used in previous studies on HF and never used to evaluate model effectiveness.

3. Aims of the Study

The primary aim of this study is to determine the long-term efficacy of an interdisciplinary DMP involving cardiologist, primary care physician and nurse, combining pre- and post-discharge care and following patients for two years. The secondary aim is to evaluate if the frailty profile should be useful to identify which HF elderly patient may benefit mostly from a DMP and select the appropriate model of care.

4. Study plan, Patients and methods

Objectives. The study is designed as a randomized open trial conducted at two hospital heart failure clinics, comparing a DMP and usual care (UC). The primary end-point of the study is the composite of death from any cause and hospital admissions for heart failure. Other planned outcome variables are all-cause and heart failure hospitalizations, the cumulative number of hospitalizations, all-cause and heart failure related mortality, quality of life, perceived health status, functional status and indexes of quality of care, such as the percentage of patients receiving beta-blockers.

Eligibility of patients.

Inclusion criteria are as follows: age 70 years or more and discharged home after a hospitalisation due to heart failure, defined as an admission in New York Heart Association (NYHA) functional class III/IV of at least 24 hours requiring specific intravenous diuretic and/or inotropes or vasodilator therapy. The diagnosis will be determined according to the European Society of Cardiology guidelines (11).

Patients will be excluded if they have: 1) valvular heart disease requiring planned surgical correction, 2) active substance abuse, severe gait impairment or confined to bed, severe dementia or psychiatric disease likely to limit compliance, 3) concurrent noncardiac illness likely to reduce life expectancy, 4) need for long-term intravenous inotropic therapy, 6) unwillingness to provide informed consent, 7) living in a nursing home or outside the area served by the clinical sites.

Eligible patients will be randomised and informed consent will be given on the basis of information relevant to the allocated study group. This procedure will avoid bias arising from UC patients being informed of the intervention strategy. It is presumed that this information is likely to influence outcome as some controls would employ the intervention strategy on their own initiative.

Measurments.

In both groups initial assessment will include history, physical examination and a multidimensional assessment (12) including education, marital status, financial income, social and emotional support, ability to perform basic (BADL) and instrumental (IADL) activities of daily living (13,14), cognitive status measure by means of the Folstein Mini Mental Status Examination, depressive symptoms measured by means of the Geriatric Depression scale, comorbidity will be quantified with the Charlson Comorbidity index (15), quality of life and self-perceived health, evaluated, respectively with the Minnesota Living with Heart Failure (MLwHF), a 5-item scale (from very good to very poor) and the EuroQOL (16). Disability is defined as an impairment in at least two IADL or at least one BADL.

An ad-hoc translated and validated local version of the European Self Care Behaviour scale (ESCB) will be administered in order to evaluate the baseline level of self-care (17). Frailty is measured by means of a modified frailty score (FS) (22), calculated combining five domains of functioning (age over 80, cognitive impairment defined as a MMSE score \leq 24, reduced mobility, urinary incontinence and physical impairment defined as a NYHA functional class III-IV) into six stages of increasing impairment. Stage 1 included patients <80 years, in II NYHA class and without impairments in mobility, continence, or cognitive function. Stages 2 to 6 included patients with the presence of one, two, three, four or all of the specific items, respectively. The risk profile of each patient will be also calculated by means of a prognostic score index .

Intervention

All patients will be discharged on optimized therapy and will receive before randomization a detailed summary and a standardized educational program focused on low-salt diet and drug therapy, self monitoring of blood pressure and symptoms, daily weight, smoke cessation, fluid intake and daily physical activity.

DMP Group. The program is based on a hybrid model, combining hospital clinic- and home-based care. In each of the two participating teams, the members will be a cardiologist experienced in geriatrics, two-to-four specialized nurses and the patient's primary care physician. According to ESC guidelines, the components of the program are: discharge planning, continuing education, therapy optimization, improved communication with health care providers, early attention to signs and symptoms and flexible diuretic regimen (11).

A written list of recommendations, a weight chart, a contact number available 6 hours/day and an educational booklet will be provided only to these patients. They will be encouraged to present their discharge/visit summary and weight chart at all visits. Follow-up is based on hospital clinic visits, periodical nurse's phone calls and home or office primary physician visits.

The cardiologists are the case managers, designed and documented the treatment plan. Hospital visits will occur in the heart failure clinics within 7 to 14 days from discharge and, therefore at 1, 3 and subsequently each 6 months. At each visits patients will receive reinforcement of education and optimization of therapy. Nurses will made follow-up phone calls to patients, receive the patient's calls and contacted patients when they did not present to scheduled visits. They could not modify therapy, however, they could recommend that the patient consults the cardiologist or primary care physician when the patient's status deteriorated abruptly or the patient experienced a significant problem

requiring prompt attention. The nurses also play a pivotal role in education program and coordination of patient's management. The primary care physicians are asked to assess adherence to treatment, evaluate possible adverse drug reactions and identify and possibly treat at home signs of worsening clinical condition, concurrent infections or comorbidities and potential precipitating factors, as well as dietary regimen. They will manage all problems not related to heart failure, receive regular written updates from the hospital team and will be notified of abnormal laboratory and clinical values.

Usual care. After discharge, patients assigned to UC will receive all treatments and services ordered by their primary care physician and/or personal cardiologist. The baseline clinical evaluation and therapeutic plan are documented in the patient's chart. In this group vital status and events are recorded by means of phone calls performed every six months.

Outcomes. Patients will be followed for at least two years and outcome data will be obtained at every visit. All in- and outpatient activities are monitored through medical records and contacts with primary care physicians. All patients were followed for two years and clinical status, medications, number of primary care and specialist visits and events were recorded at each visit or phone call. Events were collected also using phone calls, hospital and administrative databases . Outcomes are evaluated in a blinded manner by a central endpoint committee composed of three cardiologists, who have no knowledge of the treatment assignment. Two members will independently evaluate all cases. In the event of a discrepant classification, the third member reviews the report and assigns the final classification. All MA questionnaires will be analyzed in a blinded fashion.

Estimation of costs. In this study the National Health System (NHS) perspective will be adopted, as in Italy it provides all health care services for patients affected by moderate-to-severe HF. Data on resource utilization will be collected prospectively and will only comprise direct costs (pre-discharge education, medications, management program and usual care and hospitalizations) calculated on the basis of NHS charges at the time of the study and stratified according to the level of frailty. The costs of the hospital-based outpatient program are derived on the basis of the total of telephone calls (mean 15 minutes each) and visits (mean 30 minutes each). The average cost for one HF hospitalization, according to standard mean tariff for Diagnosis-Related Group (DRG) 127 at the time of the study is € 3184.26. For non-HF related admissions, individual DRG tariffs will also be calculated. The initial admission is not included in the cost analysis.

The costs of daily medical therapy (digitalis glycosides, diuretics, beta-blockers, calcium channel blockers, other vasodilators, anti-arrhythmic drugs, ACE inhibitors, angiotensin receptor blockers and anticoagulants), will be estimated using the average dose of therapy to calculate the number of tablets

taken during the follow-up and multiplying this number by the cost per tablet reported in the annual National Therapeutic Formulary. These costs will be actualized by assuming an annual rate of increase of 5%. Indirect costs are difficult to evaluate and will not be considered.

Economic analysis. Economic analysis is based on cost-effectiveness analysis (CEA), in which the alternative interventions are examined in the light of total cost per unit of health outcome. Incremental cost-effectiveness ratios will be calculated for the different frailty profiles, as the cost incurred to prevent one event, given that there was a significant reduction in the primary and secondary end-point, all-cause- and HF-related admissions, non-HF related admissions between groups. The time horizon will be equivalent to that observed during the period of the study (ie, no future projections are made). Moreover, a cost-utility analysis is programmed, calculating quality-adjusted life years (QALY) for each intervention group using the survival method and EuroQOL index as utility. To examine the impact of change in one or more variables on the results of the analysis, a sensitivity analysis where the cost of DMP and hospitalizations are changed of $\pm 10\%$ will be performed.

Study sample.

Based on previous studies (5,6), metanalyses (7-10) and national databases (3), the study sample is calculated to detect at least a 40% relative reduction at two years in the outcome of death and/or unplanned readmission for heart failure in the DMP, based on the assumption of a 60% event rate for the control group with a 0,05 alpha and 0,90 power. The planned sample size is at least 92 patients per group or, alternatively, the occurrence of 88 events.

Statistical Analysis.

In the primary Study, the two groups will be compared by the t test for normally distributed continuous variables and the chi square test for normal variables (with calculation of odds ratio [OR] and 95% confidence intervals [CI] where appropriate) and the Fisher exact test for variables with a prevalence <5%. Analyses are conducted according to an intention-to-treat approach. Kaplan-Meier survival curves are constructed to assess differences in deaths or readmissions between groups and compared using the log rank test. Data for all event-free patients are censored on study day 730. Event-free survivals are tested with the Cox proportional hazards method. Logistic regression analysis will be performed in order to identify factor potentially related to non-adherence to the program.

In the Secondary Study: Groups will be compared by the t test for normally distributed continuous variables (with Bonferroni correction as appropriate) and the chi square test and Fisher exact test for

nominal variables. The predictive value of the Frailty Score and prognostic score index for the primary end-point will be compared by means of receiver operating curves (ROC). The intervention groups and frailty subgroups will be compared using multiple Cox proportional-hazards models, without and with adjustment for potentially confounding variables: age, sex, NYHA III-IV class, ischemic etiology, diabetes mellitus, atrial fibrillation, systolic blood pressure <100 mmHg, ejection fraction, anemia (hemoglobin ≤ 12 g/dl), serum sodium and creatinine levels, beta-blocker and ACE-inhibitor or Angiotensin receptor blockers treatment. NYHA III-IV class was not included in multivariable analysis of patients in stage 1 and stages 4-6. Differences in treatment effects according to frailty subgroups will be evaluated by tests of interaction and the statistical significance determined by a Wald chi-square test for interaction. Effects will be omitted from tables when a too small number of events were observed in the given analysis.

All analyses will be performed using SPSS for Windows (SPSS Inc. USA).

5. Variables collected

1. Baseline Demographic Characteristics and Multidimensional assessment.

Age (years) Gender (% Males) Education (years) Single/widowed/divorced (%) Living alone (%) Low financial income* No social/family support ≥2 IADL dependency** ≥1 BADL dependency** MMSE score Mean GDS 15 score

2. Baseline Clinical Characteristics

Body Mass Index (Kg/m²) Systolic Blood pressure (mmHG) Heart rate (b/min) Heart Failure etiology (Ischemic, Hypertensive, Dilated, Valvular, Other/multiple) Charlson comorbidity index § Comorbidities (Hypertension, Diabetes mellitus, Previous myocardial infarction, COPD NYHA class at discharge Mean LVEF (%) Serum Sodium (mmol/l) Creatinine clearance (ml/min) Hemoglobin (g/dl) Treatments at discharge: ACE-inhibitors, Angiotensin receptor blocker, Beta-blockers, Mean daily furosemide dose (mg), Spironolactone, Digoxin, Amiodarone, Nitrates, Anticoagulants

3. Outcomes.

Primary outcome variable: death from any cause and/or hospital admissions for HF. Secondary end-points: total and cardiovascular mortality, all-cause and HF-related admissions Costs of care

4. Quality of life and functional status.

Modified Frailty Score: Stage 1-6 EuroQol Index Mean ESCBs score

5. Quality of care.

Clinical status (NYHA)

Number of primary care and specialist visits, Electrocardiograms and echocardiograms, Number of telephone calls, number of home primary care visits, Medications,ACE-inhibitors and Beta-blockers at follow-up

6. Estimate of costs.

Pre-discharge Education

Medications Echocardiography Cardiology visits Telephone support Primary Care office visits Primary Care home visits Total outpatient cost, Mean outpatient cost (Standard deviation) HF admissions, Non HF admissions, All-cause admissions Total inpatient cost, Mean inpatient cost (Standard deviation) Total costs, Mean total costs , (Standard deviation) Mean saving per patient (delta DMP-UC total costs)

7. Economic analysis

CEA (ICER) QUALY

Ethical issues

The protocol is consistent with the principles of the Declaration of Helsinki and all participants will gave their written informed consent. No Institutional Review Board review for this type of study (non pharmacological trial) is required for at the time of study in our Institution.

Coordination of the Study

Executive Committee: [name]*, [name] ** MD,

Steering Committee: [name]*, [name] ** MD, [name]***, MD, [name]#, MD, [name]**, MD, [name]*, MD.

End-point Committee: [name]^{**}, MD, FESC, [name]^{**}, [name]§.

Statistical Analysis: [name]§, MA, PhD; §§

Researchers: [name]*, [name] ** , [name]**, [name]**, MD **[name]*, RN, [name]**, RN, [name]**, RN, [name]*, RN, [name]** RN, [name]**, RN, [name]**, RN, [name]*, RN,

* Heart Failure Unit, Division of Cardiology, INRCA Institute of Care and Research for Elderly, Rome, Italy.

**Heart Failure Clinic, Division of Cardiology/C.C.U., San Camillo Hospital, Rome, Italy

***Cardiovascular Center and University, Trieste, Italy

#Heart Failure Clinic, Division of Cardiology, San Martino Hospital, Belluno, Italy.

§ Heart Failure Clinic, Division of Cardiology, Villa Bianca Hospital, Trento, Italy.

§§Department of Public Health and Microbiology, University of Turin, Turin, Italy

Participating Centers

* Heart Failure Unit, Division of Cardiology, INRCA Institute of Care and Research for Elderly, Rome, Italy.
**Heart Failure Clinic, Division of Cardiology/C.C.U., San Camillo Hospital, Rome, Italy [name] [name]
[name], FESC
[name]
Tel: [name]

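### Consent follows allocation and differs by arm while refusal of consent is an exclusion, so as written refusers are randomised and then excluded, contrary to the stated intention-to-treat analysis

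*Protocol*

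**What the plan says.** Under Eligibility of patients (section 4), the order is allocation first and consent second, with different information for each arm: "Eligible patients will be randomised and informed consent will be given on the basis of information relevant to the allocated study group". The reason given is contamination: "This procedure will avoid bias arising from UC patients being informed of the intervention strategy".

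The exclusion list in the same subsection contains "6) unwillingness to provide informed consent". Ethical issues adds that "all participants will gave their written informed consent". Statistical Analysis says "Analyses are conducted according to an intention-to-treat approach".

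Nowhere does the protocol describe a consent obtained before allocation, or say what happens to the data of a patient who refuses after allocation. The sample size in Study sample carries no stated allowance for refusal.

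**The concern.** An exclusion criterion should be settled before allocation. Here the only consent described depends on the arm, so willingness to give it cannot be known until the arm is known. A patient who then refuses has been randomised and also meets an exclusion.

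The two requests are not alike. DMP patients are asked to accept clinic visits at 7 to 14 days, at 1 and 3 months and six-monthly after that, together with nurse calls and primary-physician visits. UC patients are followed by a phone call every six months. Both arms have the baseline multidimensional assessment. Refusal may therefore differ between arms in number and in type of patient. If refusers leave the analysis, the primary end-point is compared between two groups that randomisation no longer makes comparable.

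**Working it through.** **Text side by side**

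1. Consent content depends on the allocated arm, so consent follows allocation.
2. Refusal of consent is exclusion 6.
3. No other consent is described, so exclusion 6 is applied after allocation.
4. Intention-to-treat requires every randomised patient to be analysed in the allocated arm. Steps 1 to 3 exclude some of them, so the two rules conflict.

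**The planned size, for reference**

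Study sample gives the inputs: "based on the assumption of a 60% event rate for the control group with a 0,05 alpha and 0,90 power", and "at least a 40% relative reduction at two years".

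- DMP event rate: 0.60 × (1 − 0.40) = 0.36.
- Exponential hazard ratio: ln(0.64)/ln(0.40) = 0.487.
- Freedman events, two-sided 0.05, power 0.90: (1.960 + 1.282)² × [(1 + 0.487)/(1 − 0.487)]² = 88.3.
- Per group: 88.3/(0.60 + 0.36) = 92.0.

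This reproduces "The planned sample size is at least 92 patients per group or, alternatively, the occurrence of 88 events". The calculation is internally sound and has no refusal term.

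**What removing refusers could do**

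Assumptions, none of them from the protocol: no true effect; 60% events in both arms; 92 randomised per arm; 2% refuse in UC; a share r refuses in DMP; refusers have event risk q and are dropped.

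The rate among those analysed is (0.60 − r × q)/(1 − r).

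The chance of a two-sided 0.05 result favouring DMP is Φ[(d − 1.96 × SE₀)/SE₁]. Here d is UC minus DMP, and SE₀ and SE₁ are the pooled and unpooled standard errors.

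Worked case, r = 0.20 and q = 0.80:
- DMP: (0.60 − 0.16)/0.80 = 0.550, with 92 × 0.80 = 73.6 analysed.
- UC: (0.60 − 0.016)/0.98 = 0.596, with 92 × 0.98 = 90.2 analysed.
- d = 0.046 and both standard errors are 0.078, so the chance is 8.6%.

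| DMP refusal | Refuser risk | DMP rate | UC rate | Chance of a significant result favouring DMP |
|---|---|---|---|---|
| 10% | 80% | 57.8% | 59.6% | about 4% |
| 20% | 80% | 55.0% | 59.6% | about 9% |
| 20% | 70% | 57.5% | 59.8% | about 5% |
| 20% | 60% | 60.0% | 60.0% | 2.5% (nominal) |
| 20% | 40% | 65.0% | 60.4% | about 0.5% |

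The sign of the bias turns on whether refusers are at higher or lower risk than the average patient.

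**What keeping decliners costs**

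Assume the planned effect holds in accepters and DMP decliners have the 60% control risk. The DMP rate is then 0.36 × (1 − r) + 0.60 × r. Power is for the two-proportion test at 92 per group. N is per group for 90% power by the same test.

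| DMP declining | DMP rate | Power at 92 per group | N per group for 90% power |
|---|---|---|---|
| 0% | 36.0% | 0.91 | 89 |
| 5% | 37.2% | 0.88 | 99 |
| 10% | 38.4% | 0.84 | 111 |
| 20% | 40.8% | 0.74 | 141 |

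**The case against.** - **The order is deliberate.** Arm-specific consent has a stated purpose, to keep UC patients from learning of the intervention. That stands as a reason for not describing the DMP to them. It is no reason to exclude a randomised patient.
- **Eligible might already mean willing.** Exclusion 6 is listed before the sentence on randomising eligible patients, so a general unwillingness might be screened first. The protocol describes no such step. If one exists, it needs to be written in.
- **Nothing says refusers are dropped.** This is correct. Statistical Analysis claims intention-to-treat, and Outcomes says events are also collected from hospital and administrative databases, so a refuser's outcome might be obtainable if data use is permitted. Removal is implied by exclusion 6, not stated. The consent statement under Ethical issues adds little, since a refuser may simply not count as a participant.
- **A reader might infer that the bias favours DMP**, on the view that frailer or less adherent patients decline it. The Introduction links frailty to low compliance, but low compliance is not refusal of consent. The exclusions already remove severe gait impairment, bed confinement, severe dementia and life-limiting illness. Fitter patients could equally decline the visits, and the bias would then run against DMP. The protocol does not support either direction.

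**Conclusion.** The conflict is in the text and needs correcting: as written, exclusion 6 operates after allocation, on information that differs by arm, and cannot stand beside an intention-to-treat analysis of everyone randomised. This is a matter for the protocol rather than an analysis plan, because the timing and scope of consent decide whose data may be used at all.

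The size and direction of any bias are unknown. Under the assumed 20% v 2% refusal with no true effect, the chance of a false result favouring DMP ranges from about 0.5% to about 9% as refuser risk goes from 40% to 80%. With 10% v 2% refusal and 80% risk it is about 4%. These figures rest entirely on assumed refusal rates and risks, and on refusers actually being removed. They show that the rule can matter; they do not estimate its effect in this trial.

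**What to change.** Amend Eligibility of patients and Statistical Analysis as follows.

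1. Before randomisation, obtain arm-neutral consent to the baseline assessment, follow-up calls and use of hospital and administrative records, without describing the DMP. Apply exclusion 6 only at this step. All patients already receive an educational program before randomisation, so a contact exists at which to ask.
2. After allocation, ask DMP patients for consent to the programme.
3. State that all randomised patients are analysed in their allocated arm, and that those who decline the programme are followed by calls and databases as far as their consent permits.
4. Report refusals by arm.
5. Restate the 0.90 power with an assumed decline rate, and enlarge the sample if that rate is material.

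The direct cost is a second consent form and an amendment. UC patients still do not hear of the intervention, so the contamination safeguard is kept. By the same token, patients would still be randomised without having been told about the DMP, and the ethical justification for that should be set out. Dilution is the other cost, and it is not negligible if many decline: the last table under the working gives 111 per group at 10% and 141 at 20%, in place of 92.

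### On the natural reading, only drug costs rise by an assumed 5% a year while HF admissions stay at one tariff, so cost totals mix price bases; separately, the saving row is labelled with the opposite sign

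*Protocol*

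**What the plan says.** The Protocol's paragraph on Estimation of costs (section 4) sets a general basis for direct costs: they are "calculated on the basis of NHS charges at the time of the study".

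It then gives item rules:

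- HF admissions: the "standard mean tariff for Diagnosis-Related Group (DRG) 127 at the time of the study is € 3184.26".
- Non-HF admissions: "For non-HF related admissions, individual DRG tariffs will also be calculated".
- Drugs: tablets taken during follow-up are counted and costed by "multiplying this number by the cost per tablet reported in the annual National Therapeutic Formulary". The next sentence reads: "These costs will be actualized by assuming an annual rate of increase of 5" per cent.

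No indexation is stated for admissions, visits or telephone calls where those items are described. Neither a common price year nor a formulary edition is named.

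The Economic analysis paragraph restricts the time horizon to the observed study period and rules out projection. It plans incremental cost-effectiveness ratios by frailty profile and a cost-utility analysis.

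The list of cost variables (Variables collected, item 6, Estimate of costs) ends with the row "Mean saving per patient (delta DMP-UC total costs").

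**The concern.** A cost total is interpretable only if its parts are in the same year's prices. Here one component carries an assumed growth rate, while the HF admission carries a single tariff with no growth. The total, the between-arm difference and every ratio built on it inherit the mixture.

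The 5% rule also sits awkwardly with the protocol's own framework. Charges of the study period are said to apply, and nothing is projected beyond that period, so it is unclear what an assumed price trend is for.

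The saving row is a separate matter of labelling. If the subtraction is carried out in the order written, a programme that saves money produces a negative saving, and one that costs more produces a positive saving. A reader of the results table could draw the opposite conclusion.

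What is at stake is the economic evaluation: costs of care are listed with the secondary end-points, and long-term cost-effectiveness is one of the questions that motivate the trial. The primary end-point and the sample size are not involved.

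**Working it through.** The protocol states no cost total, saving or ratio, so there is no derived figure to reproduce. EUR 3184.26 is an input. The check therefore asks how far drug-only indexing can move the cost difference.

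**Inputs from the Protocol:** 5% a year on drug costs (natural reading); EUR 3184.26 per HF admission; two years of follow-up.

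**Assumptions, not in the Protocol:**

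- D, the yearly drug-cost difference (DMP minus usual care): EUR -100 to +600.
- H, the difference in HF admissions per patient over two years: -0.25 or -0.5.
- e, the years from price base to patient entry: 0 or 2.
- Admissions spread evenly over the two years. Other cost items are left out.

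**Step 1, the index.** The mean two-year drug factor is F = (1.05^e + 1.05^(e+1)) / 2.

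- e = 0: (1 + 1.05)/2 = 1.025, so drug cost rises 2.5%.
- e = 2: (1.1025 + 1.157625)/2 = 1.130, so drug cost rises 13.0%.

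The admission tariff stays at 3184.26. Indexed the same way, it would be 3184.26 × 1.05 = 3343.47 after one year and 3184.26 × 1.1025 = 3510.65 after two.

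**Step 2, shift against no indexing.** The admission term cancels, leaving D × (2F - 2), that is 0.05 × D for e = 0 and 0.260 × D for e = 2.

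| D (EUR per year) | Shift, e = 0 | Shift, e = 2 |
|---|---|---|
| -100 | -5 | -26 |
| +100 | +5 | +26 |
| +300 | +15 | +78 |
| +600 | +30 | +156 |

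The sign follows the sign of D.

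**Step 3, one worked case.** D = +300, H = -0.5, e = 2:

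- Nothing indexed: 2 × 300 - 0.5 × 3184.26 = 600 - 1592.13 = -992.
- Drugs only: 300 × 2.260 - 1592.13 = 678.04 - 1592.13 = -914.
- Everything indexed: 678.04 - 1592.13 × 1.130 = 678.04 - 1799.21 = -1121.

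The mixed figure differs by 78 from the first consistent base and by 207 from the second. It lies outside the interval between the two, so it does not work as a compromise.

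**Step 4, shift against full indexing.** Here the drug term cancels, leaving -H × 3184.26 × (F - 1). This runs from 0.25 × 3184.26 × 0.025 = 20 to 0.5 × 3184.26 × 0.130 = 207. The direction depends on the admission difference.

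**Step 5, the saving row.** In the worked case with nothing indexed, DMP minus usual care is -992. The row would show a saving of -992 where the saving is +992.

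**The case against.** The best defence is that the text allows consistent readings. The 5% might bring an older drug price list up to the study period, in which case drugs and tariffs would share a base. The pronoun that opens the sentence might refer to all direct costs, which would remove the mixing. The verb might mean discounting, although a rate of increase argues against that. These readings are possible, but the sentence directly follows the drug method, and neither an edition nor a price year is fixed that would make any of them clear. The need to settle the rule stands.

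Four stronger inferences are tempting, and the document does not support them:

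- *Drug inflation is certainly counted twice.* This follows only if each year's tablets are priced from that year's edition. The protocol describes one multiplication and does not say which edition; with a single base edition, the 5% could stand in for later ones.
- *All admissions are frozen at one price.* A single figure is given for HF admissions only. Non-HF admissions use individual tariffs.
- *The result is biased against DMP.* That presumes higher drug costs under DMP. Therapy optimisation is part of the programme, but both arms are discharged on optimised therapy and the protocol gives no between-arm figure. The same price rule applies to both arms.
- *The cost difference has the wrong sign.* DMP minus usual care is the normal sign for incremental cost in a cost-effectiveness ratio. Only the word *saving* conflicts with it. The row may also be loose shorthand for a difference between the arms, but then its sign is undefined and still needs stating.

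The planned ±10% sensitivity analysis covers programme and hospital costs and does not name drug prices. Adding them would be a reasonable preference; leaving them out is not an error.

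**Conclusion.** The point holds in limited form. On the natural reading, the protocol indexes drug costs alone and so adds items on different price bases; double counting is a further possibility that depends on the unstated formulary edition. The shift in the two-year cost difference is about EUR -26 to +156 per patient against no indexing, and about EUR 20 to 207 against full indexing. Both ranges rest on the assumed drug-cost and admission differences and on entry at, or two years after, the price base. The effect is probably modest, its direction cannot be fixed from the protocol, and it is confined to secondary economic outcomes.

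The saving row is a labelling fault. It changes how one table row is read and leaves the cost-effectiveness ratio untouched.

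**What to change.** In Estimation of costs, name one price year and value every resource at it: drugs (with the formulary edition), HF and non-HF admissions, visits and calls. Drop the drug-only 5% increase. If indexing is intended, apply one rate to all cost items in both arms. If discounting is intended, say so and apply one rate to all costs in both arms and to the QALYs.

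In the list of cost variables, define mean saving as usual care minus DMP, or keep the subtraction and call the row incremental cost.

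The cost is a few sentences and one changed row label, with no new data.
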